- b. Differences in delta-values (ΔLactate/h) over time (Calculated according to the method described under method & design).
- c. Differences in time to normalization (<2 mM/L) or discharge/death.
- 2. Same question(s) as above but comparing the cohort of patients with a higher baseline lactate (>4 mmol/L) in the two treatment arms.

Hypotheses:

- 1. Restrictive fluid therapy will neither significantly affect the delta-lactate nor time to normalization in patients treated for septic shock compared with standard (more liberal) fluid therapy
- 2. Patients in septic shock with a higher baseline lactate >4mmol/L will not decrease lactate levels faster with standard fluid therapy compared with restrictive fluid therapy. This is a sub-group analysis of 1).
- 3. A high baseline lactate and/or a low Δ Lactate/h is associated with a higher mortality irrespective of fluid treatment.

Outcome measure(s)

- 1. Primary outcomes are the differences in plasma lactate concentrations and Δ Lactate/h during the first 72 hours between the two treatment arms in the CLASSIC trial.
- 2. Secondary outcomes are the time to normalization of lactate, length of intensive care unit (ICU) stay and 90-day mortality in restrictive vs standard group of the CLASSIC trial.

The CLASSIC trial protocol Page 73/82

Method and design

All retrospective serial time-stamped point-of-care blood gas analyses from patients included in the CLASSIC trial will be collected and analyzed for the first 72 hours or until death or discharge from the ICU (depending on the availability from the centers).

Baseline characteristics (age, sex, body weight, pre-existing conditions and lab), daily fluid balance, urine output, treatment (mechanical ventilation, renal replacement therapy, vasopressors) and 90-day mortality data of included patients will be available from the CLASSIC trial database.

Normally distributed continuous data will be presented as mean +/- standard deviation and independent Student's t test will be used to compare means. Mann-Whitney U test will be used to compare mean ranks between groups if data shows non-normality assessed by the Shapiro-Wilk test. Such data will be presented as median (interquartile range). Data of categorical variables will be analyzed with Chi-square or Fisher's exact test as appropriate. A P-value of <0,05 will be considered as a statistically significant difference between groups for the primary outcomes.

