ΔLactate/h is defined as (baseline lactate/baseline lactate – subsequent lactate) / baseline lactate x (100 / time interval(h)). Baseline lactate value is the lactate concentration at the time of randomization (from the electronic case report form). We will compare the groups using a mixed model for repeated measures to deal with missing values. Logistic multiple regression analysis for baseline lactate, ΔLactate/h and mortality adjusted for allocation treatment group and important risk factors (age, co-morbidities, severity of disease et cetera).

Centers will provide data in pseudonymized form. Data will be stored in an encrypted hard drive. Key for decryption and identification will be stored in a fire safe locked cabinet.

Sample size estimate

The Swedish centers have to date included 130 patients. Outside of Sweden the two hospital regions of Zealand, Denmark have included 604 patients and the University Hospital of Pilsen, Czech Republic, have included 50 patients. The estimated sample size will all together consist of 784 patients. The number of blood gas analyses will vary depending on patient and including center.

References:

- 1. Singer M et al (2016) The Third Inter- national Consensus definitions for sepsis and septic shock (Sepsis-3). JAMA 315(8):801–810
- 2. Evans L et al, Surviving sepsis campaign: international guidelines for management of sepsis and septic shock 2021, Intensive Care Medicine (2021) 47:1181–1247

The CLASSIC trial protocol Page 74/82

- 3. Vincent JL et al, The value of blood lactate kinetics in critically ill patients: a systematic review. Crit Care 2016:20;257
- 4. Hernandez G et al, The ten pitfalls of lactate clearance in sepsis, Intensive Care Medicine (2019) 45: 82-85
- 5. Garcia-Alvarez et al, Sepsis-associated hyperlactatemia, Critical Care 2014, 18:503
- 6. Jansen TC et al, LACTATE study group. Early lactate guide-therapy in intensive care unit patients: a multicenter, open-label, randomized controlled trial. Am J Respir Crit Care Med 2010;182:752-761.
- 7. Hjortrup et al, Effects of Fluid Restriction on measures of circulatory efficacy in adults with septic shock. Acta Anaesthesiol Scand 2017 Apr;61(4):390-398

The CLASSIC trial protocol Page 75/82

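### Lactate sub-study: mortality is regressed on a lactate change whose window can be closed by death or ICU discharge, with no fixed predictor time, no at-risk set and no interaction with allocation

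*Protocol*

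**What the plan says.** All of this is in the lactate sub-study, Protocol 14.8.1.b.

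- **Hypothesis 3:** a high baseline lactate and/or a low ΔLactate/h "is associated with a higher mortality irrespective of fluid treatment".
- **Data:** retrospective, time-stamped blood gases, collected "for the first 72 hours or until death or discharge from the ICU" and "depending on the availability from the centers".
- **Predictor:** a percentage change from baseline per hour. The printed definition ends "subsequent lactate) / baseline lactate x (100 / time interval(h" (closing brackets omitted). On the starting value it says "Baseline lactate value is the lactate concentration at the time of randomization". It does not identify the subsequent lactate.
- **Mortality model:** logistic regression of baseline lactate, ΔLactate/h "and mortality adjusted for allocation treatment group and important risk factors". No horizon is given in that sentence, although the same section says that 90-day mortality is available from the trial database.
- **Arm comparison:** "We will compare the groups using a mixed model for repeated measures to deal with missing values". This model is for the randomised comparison of lactate, not for the mortality regression.
- **Outcomes:** the primary outcomes are the between-arm differences in lactate and ΔLactate/h. Mortality is a secondary outcome only as restrictive versus standard.

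No landmark, at-risk set or interaction with allocation is specified.

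**The concern.** A prognostic regression needs a predictor that is complete before the outcome clock starts, in people still at risk at that point. Here the predictor may be completed at any time up to 72 h, and death, which is the outcome, is one of the events that can complete it. Two distortions follow.

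- **Numerator.** If the last available value is used and lactate climbs shortly before death, early deaths contribute their own terminal rise.
- **Denominator.** The same relative change over a shorter window gives a larger hourly rate, whichever event shortened the window. Live discharge also shortens it, in survivors.

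Adjusting for age, co-morbidity, severity and allocation removes neither, because the problem is the timing of the measurement relative to the event.

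The second issue is the phrase about fluid treatment. A model with allocation as a main effect assumes a common lactate slope in the two arms. It cannot be used to conclude that the slopes agree.

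At stake is the credibility of the ΔLactate/h part of hypothesis 3. The reported association could be exaggerated, absent in truth, or masked.

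**Working it through.** **1. The plan's own figure.** The sub-study size is the sum of its centres: 130 + 604 + 50 = 784, as stated. It gives no power, effect size or odds ratio, so there is no inferential figure to reproduce.

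**2. The formula.** Taking the evident intention, ΔLactate/h = (baseline − subsequent) / baseline × 100 / hours. As printed it has a stray extra baseline term, which must be corrected before it can be computed. For an illustrative 40% fall:

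- over 72 h: 40 / 72 = 0.56% per hour
- over 12 h: 40 / 12 = 3.33% per hour

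The same relative fall differs sixfold through the window alone. A terminal rise of 0.3 times baseline at 12 h gives −30 / 12 = −2.5% per hour. An early death can therefore lie at either extreme.

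**3. Simulation inputs.**

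- From the documents: N = 784; 45% control mortality with a 15% relative reduction (Protocol 10.1.1), so 45 × 0.85 = 38.25% and pooled (45 + 38.25) / 2 = 41.6%.
- Assumed, not in the documents: 5%, 10% or 20% die within 72 h, at times uniform over 7-72 h; median terminal multiplier on lactate of 1 (no rise) to 3; 15% of survivors leave the ICU at 24-72 h; log-normal baseline lactate; exponential clearance.
- Scale: 784 × 0.05 = 39 to 784 × 0.20 = 157 early deaths, against 784 × 0.416 = 326 deaths in all, so 12% to 48% of deaths. The upper end is a wide bound.
- Model: logistic on standardised ΔLactate/h, log baseline lactate and arm; 300 runs per scenario.

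**4. Results with no true link.** Odds ratio per SD (share of runs with P<0.05):

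| Die <72 h | Terminal multiplier | Last value, no landmark | 24 h landmark | 72 h landmark |
|---|---|---|---|---|
| 5% | none | 1.01 (6%) | 1.00 (6%) | 1.00 (3%) |
| 5% | 1.5 | 0.65 (86%) | 0.97 (6%) | 0.99 (4%) |
| 5% | 3 | 0.11 (100%) | 0.94 (11%) | 0.99 (4%) |
| 10% | none | 1.12 (32%) | 1.00 (4%) | 1.00 (6%) |
| 10% | 1.5 | 0.53 (97%) | 0.95 (8%) | 1.01 (4%) |
| 10% | 3 | 0.02 (100%) | 0.88 (30%) | 1.00 (4%) |
| 20% | none | 1.30 (84%) | 0.99 (8%) | 1.00 (4%) |
| 20% | 1.5 | 0.42 (100%) | 0.90 (25%) | 1.01 (4%) |
| 20% | 3 | <0.01 (100%) | 0.78 (81%) | 1.00 (6%) |

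The 24 h landmark moves off 1 because in these runs the rise is already present at 24 h in those who die before 30 h. That value does precede the death, but a few imminent deaths drive the estimate. The 72 h result is near 1 by construction, since no rise was modelled for later deaths.

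**5. Other settings.**

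- Smaller rise (0.3-1.0 times baseline), with 5%, 10% and 15% dying before 72 h: last value 0.68, 0.48 and 0.31; 24 h landmark 0.97-0.99.
- Similar inputs with exponential clearance: last value 0.61, 0.39 and 0.25 with the rise, and 1.08, 1.16 and 1.26 without it. With the rise and no landmark, a 6 h value gives about 1.0 (P<0.05 in 2-6% of runs) and a 12 h value 0.94-0.84.

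**6. With a true link.** In the step 3 setting, the 72 h landmark gives 0.82-0.84. The last value gives 0.47 to below 0.1 with a terminal rise, and 0.87, 0.98 and 1.16 (5%, 10%, 20% early deaths) without one. The open window can exaggerate, hide or reverse a real association.

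**7. Interaction.** The planned form is logit(p) = α + β₁Δ + β₂L₀ + γ·arm + risk factors, with a single β₁ for both arms. Testing equality needs a term δ·arm×Δ. With equal arms each slope has about twice the variance of the common slope, so their difference has about four times the variance and twice the standard error. A non-significant δ is therefore weak evidence of equality, and its confidence interval is what matters.

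**The case against.** The strongest reply is that the protocol never says that the last value before death enters the model. It speaks of a subsequent lactate and of changes over time. If an early fixed value were used, the bias would be small (about 1.0 at 6 h in step 5). This stands, and it rules out a tempting stronger reading: that the analysis itself creates the association and would confirm hypothesis 3 whatever the truth. The documents do not support that. They leave the predictor time open, give neither the share dying within 72 h nor any terminal lactate data, and cite 34 observational studies in which falling lactate went with lower mortality (without saying whether those used a landmark). The direction of the bias is not fixed either.

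Three further points have force.

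- Hypothesis 3 is and/or. Its baseline-lactate part uses a value at randomisation and has no overlap with the outcome.
- The hypothesis claims association, not prediction among those still alive, so a landmark answers a somewhat different question. It is nonetheless the question a clinician can use.
- The phrase about fluid treatment can mean no more than adjustment for allocation, which is planned. A reader might infer that the claim goes wholly untested; that follows only if the phrase means the same association in both arms.

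What the reply does not remove is the gap itself. Values are collected up to death, none is selected, and the size and sign of the result depend on that selection.

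**Conclusion.** The point holds as a defect in how the mortality regression is specified. As written, the plan permits a ΔLactate/h predictor that is partly determined by when a participant dies or leaves the ICU. The resulting association may be strongly biased, with size and direction set by choices the plan leaves open. The odds ratios above illustrate the possible range under assumed early-death shares and terminal rises; they do not predict what the sub-study will find.

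Separately, the allocation main effect cannot show a common association across arms, if that is the intended claim.

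The reach is narrow: the ΔLactate/h part of hypothesis 3 only. Baseline lactate as a predictor, the between-arm lactate comparisons and the main trial's analyses do not depend on this choice.

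**What to change.** Before the sub-study data are analysed, specify the following:

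1. **Predictor:** lactate change from randomisation to a fixed landmark, for example 24 h, with 72 h as a second landmark of equal weight. Give the sampling window around each and the corrected formula.
2. **At-risk set:** participants alive and in the ICU with a lactate at the landmark. Otherwise state how live discharges are handled, since collection stops when they leave.
3. **Outcome:** deaths after the landmark up to day 90.
4. **Accounting:** numbers excluded at each landmark through earlier death, earlier discharge or a missing sample, by arm.
5. **Model:** one model on both arms together, with allocation × ΔLactate and allocation × baseline-lactate interactions reported with confidence intervals.

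A joint model or a survival model with time-updated lactate is an alternative that avoids discarding early events.

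The cost is wording and analysis code. The blood gases are time-stamped and 90-day mortality is already held. The downside is that early deaths and early discharges leave this one analysis, so the estimate applies to patients still in the ICU at the landmark.

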14.9 Appendix 9. Preliminary results of our systematic review

Preliminary results of our systematic review on restrictive vs. standard of care/more liberal fluid resuscitation in patients with septic shock.

[figure not shown]
Pending

The CLASSIC trial protocol Page 76/82

14.10 Appendix 10. Trial flow chart

Please refer to the Consort Statement for more information (http://www.consort-statement.org/). The flowchart should be modified to reflect the flow of participants in the trial. The flowchart (n=) will be filled in at the end of the trial.

The CLASSIC trial protocol Page 77/82

14.11 Appendix 11. International Committee of Medical Journal Editors (ICMJE) form for potential conflict of interest

SAVE

ICMJE Form for Disclosure of Potential Conflicts of Interest

Instructions

The purpose of this form is to provide readers of your manuscript with information about your other interests that could influence how they receive and understand your work. The form is designed to be completed electronically and stored electronically. It contains programming that allows appropriate data display. Each author should submit a separate form and is responsible for the accuracy and completeness of the submitted information. The form is in six parts.

- Identifying information.
- The work under consideration for publication.

This section asks for information about the work that you have submitted for publication. The time frame for this reporting is that of the work itself, from the initial conception and planning to the present. The requested information is about resources that you received, either directly or indirectly (via your institution), to enable you to complete the work. Checking 'No' means that you did the work without receiving any financial support from any third party — that is, the work was supported by funds from the same institution that pays your salary and that institution did not receive third-party funds with which to pay you. If you or your institution received funds from a third party to support the work, such as a government granting agency, charitable foundation or commercial sponsor, check "Yes".

3. Relevant financial activities outside the submitted work.

This section asks about your financial relationships with entities in the bio-medical arena that could be perceived to influence, or that give the appearance of potentially influencing, what you wrote in the submitted work. You should disclose interactions with ANY entity that could be considered broadly relevant to the work. For example, if your article is about testing an epidermal growth factor receptor (EGFR) antagonist in lung cancer, you should report all associations with entities pursuing diagnostic or therapeutic strategies in cancer in general, not just in the area of EGFR or lung cancer.

Report all sources of revenue paid (or promised to be paid) directly to you or your institution on your behalf over the 36 months prior to submission of the work. This should include all monies from sources with relevance to the submitted work, not just monies from the entity that sponsored the research. Please note that your interactions with the work's sponsor that are outside the submitted work should also be listed here. If there is any question, it is usually better to disclose a relationship than not to do so.

For grants you have received for work outside the submitted work, you should disclose support ONLY from entities that could be perceived to be affected financially by the published work, such as drug companies, or foundations supported by entities that could be perceived to have a financial stake in the outcome. Public funding sources, such as government agencies, charitable foundations or academic institutions, need not be disclosed. For example, if a government agency sponsored a study in which you have been involved and drugs were provided by a pharmaceutical company, you need only list the pharmaceutical company.

4. Intellectual Property.

This section asks about patents and copyrights, whether pending, issued, licensed and/or receiving royalties.

Relationships not covered above.

Use this section to report other relationships or activities that readers could perceive to have influenced, or that give the appearance of potentially influencing, what you wrote in the submitted work.

Definitions.

Entity: government agency, foundation, commercial sponsor, academic institution, etc.

Grant: A grant from an entity, generally [but not always] paid to your organization

Personal Fees: Monies paid to you for services rendered, generally honoraria, royalties, or fees for consulting, lectures, speakers bureaus, expert testimony, employment, or other affiliations

Non-Financial Support: Examples include drugs/equipment supplied by the entity, travel paid by the entity, writing assistance, administrative support, etc. Other: Anything not covered under the previous three boxes
Pending: The patent has been filed but not issued
Issued: The patent has been issued by the agency
Licensed: The patent has been licensed to an entity, whether
earning royalties or not

Royalties: Funds are coming in to you or your institution due to your patent

1

Page 78/82

The CLASSIC trial protocol

SAVE

ICMJE Form for Disclosure of Potential Conflicts of Interest

Section 1. Identifying Inform	astion	
identifying inform	ation	
1. Given Name (First Name)	2. Surname (Last Name)	3. Date
4. Are you the corresponding author?	Yes No	
5. Manuscript Title		
6. Manuscript Identifying Number (if you kr	now it)	
Section 2. The Work Under C	onsideration for Publication	
Did you or your institution at any time rece	ive payment or services from a third party (govern	nment, commercial, private foundation, etc.) for
any aspect of the submitted work (including	but not limited to grants, data monitoring board	
statistical analysis, etc.)? Are there any relevant conflicts of interest.	est? Yes No	
Are there any relevant connicts of inter-	esti les livo	ADD
		XOD.
Section 3. Relevant financial	activities outside the submitted work.	
Place a check in the appropriate house	in the table to indicate whether you have fina	ancial salationships (sagassiless of amount
	ibed in the instructions. Use one line for each	
	port relationships that were present during	,, , , , , , , , , , , , , , , , , , , ,
Are there any relevant conflicts of interes	est? Yes No	
		ADD
Section 4. Intellectual Proper		
Intellectual Proper	rty Patents & Copyrights	
Do you have any patents, whether plan	ned, pending or issued, broadly relevant to t	he work? Yes No

SAVE

ICMJE Form for Disclosure of Potential Conflicts of Interest

Section 5.	Relationships not covered above
	relationships or activities that readers could perceive to have influenced, or that give the appearance of encing, what you wrote in the submitted work?
Yes, the follo	wing relationships/conditions/circumstances are present (explain below):
No other rela	ationships/conditions/circumstances that present a potential conflict of interest
	anuscript acceptance, journals will ask authors to confirm and, if necessary, update their disclosure statement Irnals may ask authors to disclose further information about reported relationships.
Section 6.	Disclosure Statement
below.	ove disclosures, this form will automatically generate a disclosure statement, which will appear in the box

Evaluation and Feedback

Please visit http://www.icmje.org/cgi-bin/feedback to provide feedback on your experience with completing this form.

3

14.12 Appendix 12. LOG of protocol changes

Protocol version		List of changes
Version 2.0, March 12 th	Danish Medicines	
2018	Approval	
	March 20 th 2018	
Version 2.1, May 3 rd	Approved	Protocol update after Danish Ethics
2018		Committee approval: p19 and p20
		"Ethical justification and rationale":
		detailed description of the population
		and first trial guardian.
Version 2.2, Nov 13 th ,	Approved	- Change of 3 site investigators
2018	11	- Specification in 3.4 'participant
		timeline'
		 Addition of Swedish consent
		procedures section 9.1.2
		- Updated organization diagram
		appendix 14.1
		- Specification of collection of
		consent appendix 14.5
		(addition that consent can be
		collected by medical students
		trained in the protocol)
		- Addition of Swedish consent
		procedures appendix 14.5
Version 2.3, June 19th		- Change of trial manager name
2019		- Addition of 1 Danish site
_		investigator
		- Addition of national investigator
		for Brussels
		 Specification of `End of trial' in
		new paragraph 3.5
		- Specification in 4.3 that
		withdrawal by proxy/participant
		will follow national regulations
		and those described in 4.3.1
		- Specification in 8.4 on
		reporting of serious adverse
		reactions/events.
		- Updated Steering Committee
		diagram
		- Updated definition secondary
•		outcome 'intestinal ischemia'
		- Language specification in the
		definitions of inclusion and
		exclusion criteria in 14.2
		- Language specification in one
		baseline variable in 14.2
		- Specification of acute kidney
		injury component of the
		composite secondary outcome
		'SAE', HRQoL and MoCA
		secondary outcomes in 14.2

The CLASSIC trial protocol Page 81/82

	- Specification of extracted fluid data for the interim analyses in 14.4
Version 2.4 , May 23 ^{th,} 2022	- Specification in appendix 8: updated list of CLASSIC substudies including substudy protocols

The CLASSIC trial protocol Page 82/82
